## 10.4 Expedited Adverse Event Reporting Requirements for IND/IDE Agents

10.41 **Late Phase 2 and Phase 3 Studies:** Expedited Reporting via the **ACCRU Adverse Event Expedited Report Form** for Adverse Events That Occur Within 30 Days of the Last Dose of the Investigational Agent**FDA REPORTING REQUIREMENTS FOR SERIOUS ADVERSE EVENTS (21 CFR Part 312)**

**NOTE:** Investigators **MUST** immediately report to the sponsor **ANY** Serious Adverse Events, whether or not they are considered related to the investigational agent(s)/intervention (21 CFR 312.64)

An adverse event is considered serious if it results in **ANY** of the following outcomes:

- 1) Death
- 2) A life-threatening adverse event
- 3) An adverse event that results in inpatient hospitalization or prolongation of existing hospitalization for  $\geq$  24 hours
- 4) A persistent or significant incapacity or substantial disruption of the ability to conduct normal life functions
- 5) A congenital anomaly/birth defect.
- 6) Important Medical Events (IME) that may not result in death, be life threatening, or require hospitalization may be considered serious when, based upon medical judgment, they may jeopardize the patient or subject and may require medical or surgical intervention to prevent one of the outcomes listed in this definition. (FDA, 21 CFR 312.32; ICH E2A and ICH E6).

**ALL SERIOUS** adverse events that meet the above criteria **MUST** be immediately reported to the sponsor within the timeframes detailed in the table below.

Hospitalization	Grade 1 Timeframes	Grade 2 Timeframes	Grade 3 Timeframes	Grade 4 & 5 Timeframes
Resulting in Hospitalization $\geq$ 24 hrs	7 Calendar Days			24-Hour; 3 Calendar Days
Not resulting in Hospitalization $\geq$ 24 hrs	Not required		7 Calendar Days	

**NOTE** Protocol specific exceptions to expedited reporting of serious adverse events are found in section 10.31 of the protocol.

**Expedited AE reporting timelines are defined as:**

- "24-Hour; 3 Calendar Days" - The AE must initially be reported within 24 hours of learning of the AE, followed by a complete expedited report within 3 calendar days of the initial 24-hour report.
- "7 Calendar Days" - A complete expedited report on the AE must be submitted within 7 calendar days of learning of the AE.

Serious adverse events that occur more than 30 days after the last administration of investigational agent/intervention and have an attribution of possible, probable, or definite require reporting as follows:

**Expedited 24-hour notification followed by complete report within 3 calendar days for:**

- All Grade 4, and Grade 5 AEs

**Expedited 7 calendar day reports for:**

- Grade 2 adverse events resulting in hospitalization or prolongation of hospitalization
- Grade 3 adverse events

 For studies using PET or SPECT IND agents, the AE reporting period is limited to 10 radioactive half-lives, rounded UP to the nearest whole day, after the agent/intervention was last administered.

Footnote "1" above applies after this reporting period.

Effective Date: May 5, 2011

Additional Instructions:

1. Any event that results in persistent or significant disability/incapacity, congenital anomaly, or birth defect must be reported via expedited mechanisms if the event occurs following treatment on a trial under an IND.

2. Use the ACCRU protocol number and the protocol-specific patient ID provided during trial registration on all reports.

The above expedited reports (24-hour and 3 or 7 day) must be submitted via the **ACCRU Adverse Event Expedited Report Form**.

3. Mayo Clinic Cancer Center (MCCC) Institutions: Provide copies, along with the UPIRTSO cover sheet, by fax [REDACTED] to the MCCC Regulatory Affairs Unit (RAU) Regulatory Affairs Specialist, who will determine and complete IRB reporting. The RAU will submit to the ACCRU SAE Coordinator and the ACCRU IND Coordinator to determine if FDA submission is needed.
4. Non-Mayo ACCRU Sites: Submit reports to ACCRU Safety via email at:  
[REDACTED]

Once ACCRU Safety receives the report via email, ACCRU Safety will forward a copy of the above expedited reports to the ACCRU IND Coordinator, who will notify the FDA as warranted by the event and stipulated in the U.S. Code of Federal Regulations.

Reporting serious adverse events to AstraZeneca

All Serious adverse events that meet the criteria for regulatory reporting should be copied to AstraZeneca at the same time that they are reported to regulatory authorities. The notification to AstraZeneca should include a copy of the regulatory submission and a cover page that indicates the following:

- “Notification from an Investigator-Sponsored Study”
- Study title and reference number (preferably with ISSIS reference number)
- Investigator name and address
- IND number or equivalent

Notification to AstraZeneca should also include the causality of events in relation to all study medications and if the SAE is related to disease progression, as determined by the principal investigator. The investigator is responsible for informing the IRB and/or the Regulatory Authority of the SAE per local requirements.

Send SAE report and accompanying cover page by way of fax to **AstraZeneca’s designated fax line**: [REDACTED].

In the case of blinded trials, AstraZeneca may request that the Sponsor either provide a copy of the randomization code/ code break information or unblind those SAEs which require expedited reporting.

Reporting pregnancy events to AstraZeneca

If pregnancy occurs, treatment with placebo or Selumetinib should be discontinued, and AstraZeneca should be informed of the pregnancy within one business day of the investigator or site personnel becoming aware of the pregnancy.

The outcome (spontaneous miscarriage, elective termination, normal birth or congenital abnormality) of all pregnancies occurring during treatment with placebo or Selumetinib must be followed up and documented even if the patient was discontinued from the study.

**NOTE: The Grade 4 or 5 Non-AER Reportable Events/Hospitalization Form is not being used for this study.**

**10.5 Other Required Reporting**

**10.51** Adverse events to be graded at each evaluation and pretreatment as specified in the Test Schedule (Section 4.0). The CTCAE v4.0 grading should be used unless an alternate grading method is indicated in the table below:

System Organ Class (SOC)	Adverse event/ Symptoms	Baseline	Each evaluation	Grading scale (if not CTCAE)
General disorders and administrations site conditions	Fatigue	X	X	
	Weight loss	X	X	
	Localized edema	X	X	
Gastrointestinal Disorders	Diarrhea	# of stools per day	X	
	Dyspnea	X	X	
	Nausea	X	X	
	Vomiting	X	X	
Eye Disorders	Blurred vision	X	X	
Vascular disorders	Hypertension	X	X	
Investigations	Alanine aminotransferase increase	X	X	
	Aspartate aminotransferase increase			
Skin and subcutaneous tissue disorders	Rash acneiform	X	X	
	Rash maculopapular	X	X	

10.52 Submit via appropriate Academic and Community Cancer Research United (ACCRU) Case Report Forms (i.e., paper or electronic, as applicable) the following AEs experienced by a patient and not specified in Section 10.5:

10.521 Grade 2 AEs deemed *possibly, probably, or definitely* related to the study treatment or procedure.

10.522 Grade 3 and 4 AEs regardless of attribution to the study treatment or procedure.

10.523 Grade 5 AEs (Deaths)

10.5231 Any death within 30 days of the patient's last study treatment or procedure regardless of attribution to the study treatment or procedure.

10.5232 Any death more than 30 days after the patient's last study treatment or procedure that is felt to be at least possibly treatment related must also be submitted as a Grade 5 AE, with a CTCAE type and attribution assigned.

10.53 Refer to the instructions in the Forms Packet (or electronic data entry screens, as applicable) regarding the submission of late occurring AEs following completion of the Active Monitoring Phase (i.e., compliance with Test Schedule in Section 4.0).

## 11.0 Treatment Evaluation Using RECIST Guideline

NOTE: This study uses protocol RECIST v1.1 template dated 2/16/2011 with modifications as detailed below. See the footnote for the table regarding measureable disease in Section 11.44, as it pertains to data collection and analysis.

Response and progression will be evaluated in this study using the new international criteria proposed by the revised Response Evaluation Criteria in Solid Tumors (RECIST) guidelines (version 1.1) (Eisenhauer et al., 2009) with some modifications as detailed below.

Patients with measureable tumors and patients with only non-measureable tumors ("non-target" disease only) are eligible for enrollment and will have response assessed as detailed below (**see Sections 11.43 and 11.44**).

11.1 Schedule of Evaluations: For the purposes of this study, patients should be reevaluated about 3 months (+/- 1 week) after  $^{131}\text{I}$  therapy and then every 3 months (+/- 1 week). After 12 months post-treatment, scans should be done every 6 months (+/- 2 weeks) for a maximum of 2 years (+/- 3 months) from study randomization.

### 11.2 Definitions of Measurable and Non-Measurable Disease

#### 11.21 Measurable Disease

11.211 A non-nodal lesion is considered measurable if its longest diameter can be accurately measured as  $\geq 1.0$  cm with CT scan or MRI.

11.212 A superficial non-nodal lesion is measurable if its longest diameter is  $\geq 1.0$  cm in diameter as assessed using calipers (e.g. skin nodules) or imaging. In the case of skin lesions, documentation by color photography, including a ruler to estimate the size of the lesion, is recommended.

11.213 A malignant lymph node is considered measurable if 1) it is noted to be RAI-avid on radioiodine imaging (diagnostic or post-therapy whole body scans acceptable) and it measures  $\geq 1$  cm in the long axis, 2) it is pathologically proven to be involved with thyroid cancer (by cytology or pathology) and it measures  $\geq 1$  cm in the long axis, or 3) its short axis is  $\geq 1.5$  cm when assessed by CT scan (CT scan slice thickness recommended to be no greater than 5 mm).

11.214 Tumor lesions in a previously irradiated area are considered measurable disease under the following conditions: there has been evidence of tumor progression in the irradiated area prior to study registration.

#### 11.22 Non-Measurable Disease

11.221 All other lesions (or sites of disease (e.g., visible pulmonary nodules  $<1$  cm in longest diameter)) are considered non-measurable disease. Bone lesions, leptomeningeal disease, ascites, pleural/pericardial effusions, lymphangitis cutis/pulmonis, inflammatory breast disease, and abdominal masses (not followed by CT or MRI), are considered as non-measurable as well.

Note: 'Cystic lesions' thought to represent cystic metastases can be considered as measurable lesions, if they meet the definition of measurability described above. However, if non-cystic lesions are present in the same patient, these are preferred for selection as target lesions.

#### 11.3 Guidelines for Evaluation of Measurable Disease

##### 11.31 Measurement Methods:

- All measurements should be recorded in metric notation (i.e., decimal fractions of centimeters) using a ruler or calipers.
- The same method of assessment and the same technique must be used to characterize each identified and reported lesion at baseline and during follow-up.
- Imaging-based evaluation is preferred to evaluation by clinical examination when both methods have been used at the same evaluation to assess the antitumor effect of a treatment.

##### 11.32 Acceptable Modalities for Measurable Disease:

- Conventional CT and MRI: This guideline has defined measurability of lesions on CT scan based on the assumption that CT slice thickness is 5 mm or less. If CT scans have slice thickness greater than 5 mm, the minimum size for a measurable lesion should be twice the slice thickness.

- As with CT, if an MRI is performed, the technical specifications of the scanning sequences used should be optimized for the evaluation of the type and site of disease. The lesions should be measured on the same pulse sequence. Ideally, the same type of scanner should be used and the image acquisition protocol should be followed as closely as possible to prior scans. Body scans should be performed with breath-hold scanning techniques, if possible.
- FDG-PET: FDG-PET scanning is allowed to complement CT scanning in assessment of progressive disease [PD] and particularly possible 'new' disease. A 'positive' FDG-PET scanned lesion is defined as one which is FDG avid with an uptake greater than twice that of the surrounding tissue on the attenuation corrected image; otherwise, an FDG-PET scanned lesion is considered 'negative.' New lesions on the basis of FDG-PET imaging can be identified according to the following algorithm:
  - a. Negative FDG-PET at baseline with a positive FDG-PET at follow-up is a sign of PD based on a new lesion.
  - b. No FDG-PET at baseline and a positive FDG-PET at follow-up:
    - i. If the positive FDG-PET at follow-up corresponds to a new site of disease confirmed by CT or MRI, this is PD.
    - ii. If the positive FDG-PET at follow-up is not confirmed as a new site of disease on CT at the same evaluation, additional follow-up CT scans (i.e., additional follow-up scans at least 4 weeks later) are needed to determine if there is truly progression occurring at that site. In this situation, the date of PD will be the date of the initial abnormal PDG-PET scan.
    - iii. If the positive FDG-PET at follow-up corresponds to a pre-existing site of disease on CT that is not progressing on the basis of the anatomic images, it is not classified as PD.

### 11.33 Measurement at Follow-up Evaluation:

- Cytologic and histologic techniques can be used to differentiate between PR and CR in rare cases (e.g., residual lesions in tumor types such as germ cell tumors, where known residual benign tumors can remain.)

## 11.4 Measurement of Effect

### 11.41 Target Lesions & Target Lymph Nodes

- Measurable lesions (as defined in Section 11.21) up to a maximum of 5 lesions, representative of all involved organs, should be identified as "Target Lesions" and recorded and measured at baseline. These lesions can be non-nodal or nodal (as defined in 11.21), where no more than 2 lesions are from the same organ and no more than 2 malignant nodal lesions are selected.

**Note:** If fewer than 5 target lesions and target lymph nodes are identified (as there often will be), there is no reason to perform additional studies beyond those specified in the protocol to discover new lesions.

- Target lesions and target lymph nodes should be selected on the basis of their size, be representative of all involved sites of disease, but in addition should be those that lend themselves to reproducible repeated measurements. It may be the case that, on occasion, the largest lesion (or malignant lymph node) does not lend itself to reproducible measurements in which circumstance the next largest lesion (or malignant lymph node) which can be measured reproducibly should be selected.
- Baseline Sum of Dimensions (BSD): A sum of the longest diameter for all target lesions plus the sum of the long or short axis of all the target lymph nodes (if the lymph node qualified as a target lesion based upon a long axis of  $\geq 1$  cm, then the long axis will be used for the baseline and post-baseline assessments; if the lymph node qualified as a target lesion based upon a short axis of  $\geq 1.5$  cm, then the short axis will be used for baseline and post-baseline assessments) will be calculated and reported as the baseline sum of dimensions (BSD). The BSD will be used as reference to further characterize any objective tumor response in the measurable dimension of the disease.
- Post-Baseline Sum of the Dimensions (PBSD): A sum of the longest diameter for all target lesions plus the sum of the long or short axis of all the target lymph nodes (if the lymph node qualified as a target lesion based upon a long axis of  $\geq 1$  cm, then the long axis will be used for post-baseline assessments; if the lymph node qualified as a target lesion based upon a short axis of  $\geq 1.5$  cm, then the short axis will be used for post-baseline assessments) will be calculated and reported as the post-baseline sum of dimensions (PBSD). If the radiologist is able to provide an actual measure for the target lesion (or target lymph node), that should be recorded, even if it is below 0.5 cm. If the target lesion (or target lymph node) is believed to be present and is faintly seen but too small to measure, a default value of 0.5 cm should be assigned. If it is the opinion of the radiologist that the target lesion or target lymph node has likely disappeared, the measurement should be recorded as 0 cm.
- The minimum sum of the dimensions (MSD) is the minimum of the BSD and the PBSD.

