**11.432 Evaluation of Target Lesions**

- Complete Response (CR): All of the following must be true:
  - a. Disappearance of all target lesions.
  - b. Each target lymph node must have reduction in short axis to <1.0 cm (if short axis being used for measurement) or have reduction in long axis to < 0.7 cm (if long axis is being used for measurement).
  - c. For patients without detectable thyroglobulin antibodies, serum thyroglobulin on suppression must be measured to be <0.2 ng/ml. If a center does not have a thyroglobulin assay that reads to <2 ng/ml, then a TSH-stimulated Tg <1 ng/ml would be required to confirm complete response. For patients with detectable thyroglobulin antibodies, assessment of thyroglobulin will not be necessary for assessment of complete response.
- Partial Response (PR): At least a 30% decrease in PBSD (sum of the longest diameter for all target lesions plus the sum of the long or short axis of all the target lymph nodes (depending on which axis is being used for assessments) at current evaluation) taking as reference the BSD (see Section 11.41).
- Progression (PD): At least one of the following must be true:
  - a. At least one new malignant lesion, which also includes any lymph node that was normal at baseline (<1.0 cm short axis) and increased to  $\geq 1.0$  cm short axis and is deemed to be malignant during follow-up.
  - b. At least a 20% increase in PBSD (sum of the longest diameter for all target lesions plus the sum of the long or short axis of all the target lymph nodes (depending on which axis is being used for assessments) at current evaluation) taking as reference the MSD (Section 11.41). In addition, the PBSD must also demonstrate an absolute increase of at least 0.5 cm from the MSD.

- c. See Section 11.32 for details in regards to the requirements for PD via FDG-PET imaging.
- Stable Disease (SD): Neither sufficient shrinkage to qualify for PR, nor sufficient increase to qualify for PD taking as reference the MSD.

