#### **Overall Objective Status for Patients with Non-Measurable, Non-Target Lesions/Lymph nodes**

The overall objective status for an evaluation is determined by:

- Structural assessment of lesions/lymph nodes as detailed in Section 11.442.
- For the “non-CR/non-PD” structural category, measurement of the serum TG in the context of suppressed TSH (and negative TG antibody) will be used to determine the final response designation (the exception is for the assessment of complete response, which requires measurement of a stimulated TG, see chart below).

Non-Target Lesions & Non-Target Lymph Nodes	Serum Thyroglobulin (TG)* (or TG antibody)	New Sites of Disease	Overall Objective Status
CR	TG < 0.2 ng/ml on TSH suppression* OR stimulated TG < 0.1 ng/ml (see 11.442)	No	CR
CR	TG ≥ 0.2 ng/ml on TSH suppression* OR stimulated TG > 0.1 ng/ml (see 11.442)	No	Assess as per Non-CR/Non-PD
Non-CR/Non-PD	50% or more reduction compared to baseline Tg WITHOUT a 25% or more increase compared to the lowest TG measured on study (baseline or nadir)*	No	PR
Non-CR/Non-PD	25% or more increase compared to the lowest TG measured on study* (baseline or nadir)	No	PD
Non-CR/Non-PD	Less than 50% reduction compared to baseline TG WITHOUT a 25% or more increase compared to the lowest TG measured on study* (baseline or nadir)	No	SD
Non-CR/Non-PD	New detection of TG antibody	No	PD
Not All Evaluated	25% or more increase compared to lowest TG measured on study Tg* (baseline or nadir)	No	PD

Non-Target Lesions & Non-Target Lymph Nodes	Serum Thyroglobulin (TG)* (or TG antibody)	New Sites of Disease	Overall Objective Status
Not All Evaluated	WITHOUT 25% or more increase compared to lowest TG measured on study Tg* (baseline or nadir)	No	NE
Uequivocal PD	Any serum TG result or TG antibody result, including failure to complete the measurement as per protocol	Yes or No	PD
CR Non-CR/Non-PD Not All Evaluated	Any serum TG or TG antibody result, including failure to complete the measurement as per protocol	Yes	PD
CR Non-CR/Non-PD Not All Evaluated	TG was not evaluated or not evaluated in the context of TSH suppression*	No	NE

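### As worded, the reference sum for target-lesion progression leaves out an earlier, lower sum, so regrowth after shrinkage counts only once it is 20% and 0.5 cm above baseline

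*Combined protocol and SAP*

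**What the plan says.** Section 11.41 defines three sums for patients with target lesions. The BSD is measured at baseline. The later sum "will be calculated and reported as the post-baseline sum of dimensions (PBSD"; the section does not say whether this means one visit or all visits to date. The third is the reference for progression: "The minimum sum of the dimensions (MSD) is the minimum of the BSD and the PBSD".

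Section 11.432 then uses two references. Partial response needs a fall of at least 30% in the sum "at current evaluation) taking as reference the BSD (see Section 11.41"). Progression needs a rise of at least 20% in the sum "at current evaluation) taking as reference the MSD (Section 11.41"), with a second condition: "In addition, the PBSD must also demonstrate an absolute increase of at least 0.5 cm from the MSD". Stable disease is the remainder: "Neither sufficient shrinkage to qualify for PR, nor sufficient increase to qualify for PD taking as reference the MSD".

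For patients with non-measurable disease only, the thyroglobulin rule in Section 11.443 names its reference outright: a 25% rise "compared to the lowest TG measured on study (baseline or nadir"). No such words appear for target lesions. Section 11.0 adopts RECIST 1.1 with modifications set out in that section, and none of them announces a change in the reference for progression.

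Section 16.3 dates progression for progression-free survival (PFS) by the Section 11.0 criteria.

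**The concern.** The MSD definition names the post-baseline sum in the singular, and the progression rule glosses that sum as the one at the current evaluation. Together they leave only two candidates for the reference: baseline and today's value. The smallest sum recorded at an earlier visit has no way in.

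That matters for a patient whose target lesions shrink and then regrow. The date of progression would be late. It might never be recorded, because scheduled scans end at about 2 years from randomization (Section 11.1). Such delays need prior shrinkage, so they could occur more often in the arm with more shrinkage, and PFS is compared between arms by a log-rank test and as a 6-month rate. PFS would also mix two kinds of reference: nadir-based thyroglobulin in non-measurable disease, and in effect baseline for target lesions in measurable disease.

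**Working it through.** No figure in the plan depends on the MSD, and the sample size of 28 per arm is not involved. The check applies the written rule to example series and compares it with a nadir rule. The sums below are assumed, for illustration only.

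**Step 1. What the literal rule reduces to.** Let B be the baseline sum and C the current sum, with MSD = min(B, C).
- If C < B, then MSD = C, the increase is 0, and there is no PD.
- If C ≥ B, then MSD = B, and PD needs C ≥ 1.2B and C − B ≥ 0.5 cm.

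These are exactly the calls that B alone would give. On this reading the MSD does no work.

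**Step 2. Example series (cm).** The nadir rule uses the smallest sum before the current visit. Both rules require +20% and +0.5 cm.

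| Series | Literal MSD | Change from it | Earlier minimum | Change from it | Literal PD | Nadir PD |
|---|---|---|---|---|---|---|
| 6.0, 3.0, 7.0 | 6.0 | +17%, +1.0 | 3.0 | +133%, +4.0 | No | Yes |
| 6.0, 5.0, 6.5 | 6.0 | +8%, +0.5 | 5.0 | +30%, +1.5 | No | Yes |
| 10, 5, 6 | 6 | 0%, 0 | 5 | +20%, +1 | No | Yes |
| 10, 5, 11.9 | 10 | +19%, +1.9 | 5 | +138%, +6.9 | No | Yes |
| 10, 5, 12 | 10 | +20%, +2 | 5 | +140%, +7 | Yes | Yes |
| 10, 10.5, 12 | 10 | +20%, +2 | 10 | +20%, +2 | Yes | Yes |

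The second series never reaches a 30% reduction, so stable-disease patients are affected too. In the last series the sum never fell below baseline, and the two rules agree.

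**Step 3. How far the threshold moves.** After fractional shrinkage s, the nadir is N = (1 − s)B.
- Nadir threshold: max(1.2N, N + 0.5).
- Literal threshold: max(1.2B, B + 0.5).

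For s = 0.40, N = 0.6B. The 20% condition governs the nadir threshold when 0.2 × 0.6B ≥ 0.5, that is B ≥ 0.5/0.12 = 4.17 cm. The thresholds are then 0.72B and 1.20B, a ratio of 1.67.

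For B = 2.0 cm, N = 1.2 cm. The nadir threshold is max(1.44, 1.7) = 1.7 cm and the literal one is max(2.4, 2.5) = 2.5 cm, a ratio of 1.47.

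Where the 20% condition governs the baseline comparison (0.2B ≥ 0.5, so B ≥ 2.5 cm), the literal rule requires growth from the nadir of 1.2/r − 1, with r = N/B: 71% for r = 0.7, 140% for r = 0.5, 300% for r = 0.3.

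**Step 4. Who is exposed.** Section 16.1 plans for 40% with measurable disease: 0.40 × 56 = 22.4, or 0.40 × 28 = 11.2 per arm. Section 16.3 allows progression within 6 months after radioiodine to be disregarded at the physician's judgment, so the reference matters mostly after that.

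**The case against.** The best reply is that this is loose wording and not a rule anyone meant to apply. Section 11.41 does not confine the PBSD to the current visit. The phrase about the current evaluation in Section 11.432 can be read as saying only which sum is being tested. A minimum that always gives the same calls as baseline would be pointless, response already has its own reference, and the thyroglobulin rule has the same form with the nadir named. Nothing shows that sites or the derivation program use the literal version. As to intent, this stands: a nadir was probably meant. It does not repair the text, because no sentence says which post-baseline sums enter the MSD, and a programmer following the two sections as written would get late progression dates.

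Four stronger inferences are tempting, and the documents do not support them.
- *The MSD can never be the nadir.* It is the nadir when the sum has not fallen below baseline, and at any visit where the current sum is the lowest so far. The failure is confined to regrowth after shrinkage.
- *Only responders are affected.* The 6.0, 5.0, 6.5 cm series shows otherwise.
- *Relapse after shrinkage goes undetected.* New lesions, unequivocal non-target progression, FDG-PET findings and symptomatic deterioration trigger PD without the MSD. None of them specifically captures measured regrowth of target lesions alone.
- *A known number of patients per arm is misclassified in favour of selumetinib.* The plan gives 20% response in measurable disease for radioiodine alone but no selumetinib rate for that subgroup. Applying the overall odds ratio of 2.786 to 20% gives odds of 0.25 × 2.786 = 0.70, or 41%; adding the overall 25 points gives 45%. With 11.2 per arm that is about 2 control and 5 selumetinib responders. They are exposed to the rule; how many regrow in the relevant range before another trigger is unknown, and stable-disease patients are not counted.

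**Conclusion.** The point holds as a defect in a stated endpoint rule. As worded, after any shrinkage below baseline, target-lesion progression is judged in effect against baseline, and the MSD has no function. The conclusion rests on reading the PBSD in the MSD definition as the sum at the current evaluation, which is how Section 11.432 describes it. If the program already uses the running minimum, only the text is wrong.

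The size for an individual patient is given by the thresholds in the working. The reach is limited: mainly secondary PFS, in about 22 of 56 evaluable patients, mostly after the 6-month assessment. Confirmed best overall response could also change, since in the 10, 5, 6 cm series the third sum is PR on the literal rule and PD on the nadir rule. A delay of PD more often in the arm with more shrinkage is possible, but its size cannot be derived from the documents.

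A reader might infer that the primary result is compromised. Section 16.2 judges the 6-month response against the baseline scan, so it is largely protected. The one case to settle in words is a 6-month sum at least 30% below baseline that is also at least 20% and 0.5 cm above a 3-month nadir. This should be corrected; it does not put the primary analysis in doubt.

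**What to change.** Replace the MSD sentence in Section 11.41 with: *The MSD is the smallest of the BSD and all PBSDs recorded at evaluations before the current one.* Derive progression and stable disease in Section 11.432 from that value, keeping both the 20% and the 0.5 cm conditions.

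Leave the baseline comparison for the primary 6-month response in Section 16.2 unchanged, and say that it takes precedence for that endpoint when the same scan also meets the nadir-based progression rule.

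Check that the derivation program uses the same definition. The cost is one sentence, one clarifying clause and that check. The sums needed are already collected, and sample size and visits do not change.
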